11.4 Quality control of collected data

All data not entered directly into the survey tool (i.e., collected on paper) will be double-entered into an electronic database by two different individuals by study team members listed on the study team member page and reconciled by a third person also a study team member (e.g. [name], or the RA). Data collected on paper or by the electronic survey tool will be reviewed by the RA with the participant to ensure all items are answered. All data collected will be reviewed visually at least every three months by senior staff (e.g. [name]) to ensure quality.

9.0 Withdrawal of Subjects

All participants will be informed of the right to withdraw from the study at any time and still receive full compensation for their time. Participants can withdraw from the study at any time and withdraw their consent for us to use their PHI at any time, by notifying us in writing. Participants have been notified in the consent document that the research team will not be required to destroy or retrieve any of their or their baby's health information that has already been used or shared before their withdrawal is received. Participants will be withdrawn from the study if it becomes apparent that their participation in the study is endangering their safety or if they are found to no longer meet eligibility criteria. Failure to complete the baseline assessments may also result in withdrawal from the study.

However, failure to complete follow-up assessments or changing their mind about having a doula will not be cause for withdrawal, but will be tracked as a feasibility outcome in the study file. Participants who leave the XXX program, but who do not withdraw from the study will still be contacted to complete a final assessment, so that we can evaluate factors involved in this outcome as part of feasibility testing. Participants have given us contact information at baseline and agreed that we can contact them for follow-up assessments. This is also in the consent form. (See locator form and consent form.)

Unless participants withdraw consent at the time of being withdrawn from the study, their data may still be used in analyses. Data from participants who have withdrawn consent will be destroyed if it has not already been used.

10.0 Risks to Subjects

The primary risk posed by the assessment battery is fatigue or anxiety. Some of the assessments may stir negative memories. RAs are trained to recognize when a participant is significantly disturbed by the assessment, and will gauge participant distress by observation of outward signs (e.g. crying, shaking, pacing) and by querying the participant directly about their level of distress. Should any participant become

PROTOCOL TITLE: Providing Expanded Continuous Labor Support to Pregnant Women in New Mexico with Substance Use Disorders

significantly disturbed by the assessment (expected to be a rare or non-occurring event) they will meet with the PI or another licensed therapist (per XXX protocol) immediately following the incident to be evaluated for risk and de-escalated. (We had no instances of this with our prior study where we screened 60 participants at the XXX Clinic and conducted substantially more comprehensive and stressful baseline assessments with 33 participants.) Any participants reporting significant distress will be evaluated for suicide ideation. Any participants who indicate suicidal or homicidal ideation (expected to be a rare or non-occurring event) during an assessment and who are deemed to be in need of emergency care will be escorted to the XXX Psychiatric Emergency Room, to their counselors across the parking lot at XXX, or to XXX triage in accordance with XXX and XXX Clinic Policy.

Loss of confidentiality of sensitive information is also a risk to subjects. Participants could possibly experience social stigmatization or legal action by authorities if their answers became known outside of the research study.

It is unlikely that this research could increase social stigmatization of this greater population as a whole. In fact, it would be more likely to find results that contradict the current negative social stereotypes of pregnant women with SUD.

Physically invasive procedures are not proposed in this study. There are no known risks to having a doula provide support. There will be no financial cost to participating in the study.

Protections Against Risk

Every effort will be made to protect the confidentiality of participant records. A Certificate of Confidentiality will be automatically granted by the Federal government, because we are asking participants about the use of illegal drugs. Unfortunately, complete confidentiality can never be absolutely guaranteed because records may be examined by personnel from the XXX XXX and because accidents or other unforeseen circumstances sometimes occur despite the best protections put in place. Participants will be informed of this possibility prior to signing any consent forms for this study. All records will be kept strictly confidential and will not be inspected by any other agency except if required by law. Only research staff and staff of the XXX XXX will have access to PHI. Signed consent forms will be kept separately from any documents containing PHI or participants' unique ID numbers. The database linking ID numbers to participants' identity will be kept separately from all PHI and ID numbers and only the PI and research staff on this study will have access to this link. All hard copies of data (paper records) will be kept double-locked in rooms designated for the storage of PHI. Data will be destroyed 7 years after the last publication. The results of this research may be presented at meetings or in publications; but participants' identities will not be disclosed. All files with PII will be encrypted and password protected. Identifiable individual PHI will not be shared with non-study treatment providers.

PROTOCOL TITLE: Providing Expanded Continuous Labor Support to Pregnant Women in New Mexico with Substance Use Disorders

Support will be available to manage any anxiety or fatigue associated with the assessment for this study. Any participants reporting significant distress (expected to be rare or non-occurring) will be evaluated for suicidal ideation. Research assistants will always have a list of licensed psychologists and the number for XXX triage to call in the event of an emergency, as part of XXX policy. If a participant discloses suicidal or homicidal intentions or ongoing child or elder abuse, the research assistants will notify an available licensed psychologist who will evaluate the participant for risk and follow the state law regarding mandated reporting. In the unlikely event of significant suicide or homicide risk, XXX emergency procedures will be followed. Research assistants will disclose these limits of confidentiality to participants during the consent procedure. All participants will be informed of the right to withdraw from the study at any time and still receive full compensation for their time.

Additional Protections for Pregnant Women, Human Fetuses and Neonates are listed below.

11.0 Potential Benefits to Subjects

Participants in G1 with a doula may experience this as a benefit of increased perinatal social and emotional support. We expect this resource to benefit at least some of the participants. We expect this benefit to be enduring beyond the immediate postpartum phase, especially if it reduces the risks of postpartum SUD relapse, PTSD, or depression. However, one of the goals of this study is to test this hypothesis, thus we could find that there is no benefit associated with the doula support.

There is no direct benefit to the participants in G2 (control group) outside of the compensation provided for the study. All participants may however, benefit indirectly from the assessment session (assessment reactivity), although this is not expected to be the case for most participants. Participants will already be engaged in treatment through the XXX program. Participants may feel good about the possibility that involvement in this research may help others or themselves if in similar situations in the future.

12.0 Vulnerable Populations

Additional Protections for Pregnant Women, Human Fetuses and Neonates:

(a) Preclinical studies are not scientifically appropriate to this research as there is no pre-clinical model of doula support. Still, prior research has been conducted using substance use, social support, and mental health assessments with pregnant women with addiction, and these indicate that the risks from this type of research are minimal. Moreover, research has been conducted providing doulas to other populations of high risk women with positive results and no identified risks.

(b) Women who are in the doula group may benefit from having the services of a doula. There is no other prospect of direct benefit to the woman or fetus, but the risk to the fetus is not greater than minimal and the purpose of the research is the development of important psychosocial knowledge which cannot be obtained by any other means.

(c) Any risk in the research is the least possible for achieving the objectives of the research.

PROTOCOL TITLE: Providing Expanded Continuous Labor Support to Pregnant Women in New Mexico with Substance Use Disorders

(d) The research holds some preliminary prospect of benefit for the woman, the risk to the fetus is not greater than minimal, and the purpose of the research is the development of important psychosocial knowledge that cannot be obtained by any other means, therefore the consent of the pregnant women will be obtained in accord with the informed consent provisions of subpart A of 45 CFR 46 (46.116 General requirements for informed consent and 46.117 Documentation of informed consent).

(e) The father's consent is not required as there is no direct benefit to the fetus.

(f) Each individual providing consent under paragraph (d) or (e) of this section will be fully informed regarding the reasonably foreseeable impact of the research on the fetus or neonate.

(g) Children are not recruited in this study. Information will be collected from infant medical records, however, and adult mothers will provide consent for this.

(h) No inducements, monetary or otherwise, will be offered to terminate a pregnancy.

(i) Individuals engaged in the research will have no part in any decisions as to the timing, method, or procedures used to terminate a pregnancy. Women recruited into this study will already be at 26 weeks gestation, so termination of a pregnancy is highly unlikely.

(j) Individuals engaged in the research will have no part in determining the viability of a neonate. Women recruited into the study will already be at 26 weeks gestation, and neonatal viability is usually established earlier than this.

13.0 Community-Based Participatory Research

Involvement of the community in the design and conduct of the research.

XXX will be a key partner to this project. XXX leads policy change, research, place-based community organizing, and culture shift by and for women and people of color. Members of XXX who are listed on the IRB-approved study team in Click-IRB will have an active role in advising the design and conduct of the study and will collaborate with the team to interpret data and produce manuscripts and reports. Additionally, utilizing a community engagement framework in partnership with XXX, we will organize a small advisory group of women with an SUD who have recently given birth. They will inform the design of the doula training. These women will be individuals known to XXX and be contacted by them. Women in the advisory group will be paid \$25 in gift cards for approximately 1 hour of advising our team. Any results of the advising from XXX that results in proposed changes to the protocol or consent will be submitted to the IRB for approval before being instituted in the conduct of the study.

14.0 Sharing of Results with Subjects

Individual subject results will not be shared with participants. Participants will be informed that they may contact the study following the end of the study period (after June 30, 2019) to request copies of any peer-reviewed and published results at that time. Participants will be informed of any significant new findings that become available during the course of the study that involve the risks or benefits resulting from participating in the research or new alternatives to participation that might change their mind about participating, however we consider this to be unlikely considering the effect

PROTOCOL TITLE: Providing Expanded Continuous Labor Support to Pregnant Women in New Mexico with Substance Use Disorders

size we expect and the sample size for this pilot study. This would include findings in other research that are valid or changes in access to doulas (if they became available via Medicaid for example).

15.0 Setting

Locations where the research team will conduct the research.

Where the research team will identify and recruit potential subjects.

The research team will identify and recruit potential subjects from the XXX Clinic at XXX.

Where research procedures will be performed.

Screening, consent, and baseline assessments will occur at the XXX Clinic at HSC. In some cases, screening, consent and assessments may take place at CASAA. Pre- and postnatal doula visits will occur at either the XXX Clinic, the patients' homes, or the UNM Hospital. Births attended by doulas will occur at the UNM Hospital. Follow-up postpartum assessments will occur either at the XXX Clinic, the UNM Hospital, at CASAA, or via telephone.

16.0 Recruitment Methods

Participants will be recruited from patients being seen for appointments at the XXX clinic during regular clinic hours by study staff approved on the IRB who are not regular XXX clinic medical staff (e.g., [name] or the RA). Study staff will first ask patients who are in private rooms if they are interested in being screened for the study. Some participants may hear about the study by word of mouth as well and call our recruitment phone number.

Participants will be patients at the XXX Clinic.

Recruitment Methods

Participants will be identified by the study staff as not currently inmates (this will be determined by the presence or lack thereof of correctional officers outside the clinic room door and also by whether or not the patient is wearing orange scrubs and handcuffs). Additionally, study staff will not approach patients who are identified by medical staff as being engaged in medical treatment that render them unable to participate. This is determined as follows: before entering any patient room, our study team asks medical personnel if this is a good time to speak with the participant. This is done so that our study protocol does not interfere with medical treatment. When appropriate, medical personnel will indicate that a particular patient will not be available for screening at all that day, because it would interfere with their medical treatment. Our team will not need any more information than this.

Recruitment materials

PROTOCOL TITLE: Providing Expanded Continuous Labor Support to Pregnant Women in New Mexico with Substance Use Disorders

We will have a single flier that we will give to participants to have them contact us if when first approached they would rather contact us later. This flier will also be posted at the XXX Clinic.

Payments

Participants will receive a \$25 gift card following each of the two assessments.

17.0 Number of Subjects

We will recruit up to 34 participants in order to have 30 who complete the study. We plan to recruit 17 participants for each group in order to have 15 who complete the study in each group.

18.0 Provisions to Protect the Privacy Interests of Subjects

Screening, consent, baseline assessments, and follow-up assessments will be conducted in private rooms. Additionally, as much as possible, study questions will be conducted on laptop computers, which allows for additional privacy. Doula visits will be conducted either in private rooms at the clinic or hospital, or at the patients' homes as appropriate.

Participants will always be informed that they have a right to not answer any questions or to quit being in the study at any time. They may also take breaks or ask questions as needed at any time. Study staff are trained in building rapport with and calming participants. The electronic administration of most study questionnaires is also expected to help participants feel more at ease, as this methodology can involve less social stress than other methods of data collection.

Research staff will conduct chart reviews as outlined under section number 27 Chart Review and in accordance with XXX policy and only after receiving training and with the written consent of the participant. Research staff will access PowerChart during recruitment/screening at the clinic to identify potential participants, as described above, being seen that day at the clinic.

19.0 Consent Process

Written informed consent will be obtained at the XXX clinic or sometimes at XXX following the screen prior to any testing and will be conducted in a private room. As part of the informed consent, participants will be informed that because the research is funded by NIH there is a Certificate of Confidentiality from the Federal government. Research assistants or the PI will provide each participant with a copy of the XXX-approved consent form to read. They will be given the choice to take the form home to review or to complete consent and baseline assessments that day. Study staff will then review the consent form page-by-page as trained and, at the end of each page, ask the participant if they have any questions. At the end of the consent form, research assistants will ask the participants if they still want to be in the study. If they answer "yes," the research assistant will ask them the following questions: "What are the possible risks and benefits of this treatment?" "Can you quit being in this study at any time if you want?" "Who do you need to talk to if you have a complaint about this study?" "What information do I

PROTOCOL TITLE: Providing Expanded Continuous Labor Support to Pregnant Women in New Mexico with Substance Use Disorders

need to report if you share it with me?” The participants’ responses to the questions will be recorded verbatim on a consent record form kept in their file (see attached).

Participants will be informed of the limits of confidentiality as a part of the consent process. After participants consent to enrollment, they will sign and date the consent form and the research assistant will also sign the consent form as a witness. The participant will be provided a copy of this signed form to keep.

20.0 Chart Review

X Retrospective Chart Review

Date range of the chart review 07/01/18 – 06/30/19

Study Methods

a. XXX PowerChart

b. Only participants who have enrolled in our study and consented to have their and their newborns’ charts reviewed will have those charts reviewed.

c. Chart reviews will be conducted by XXX of the XXX Program, who is 100% faculty and is on the IRB approved study team and has Power Chart training. Data will be transferred by XXX to XXX study members via Qualtrics.

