2.0 Inclusion and Exclusion Criteria

How individuals will be screened for eligibility

Recruitment and screening will be by the RA or [name] at the XXX Clinic or in some cases at CASAA (e.g. if a participant hears about the study via word of mouth and calls our recruitment line, or if a participant is interested but is unable to be screened at the XXX Clinic) using a study specific screening form attached. See section 21 for more information on recruitment methods.

Inclusion/Exclusion Criteria

Inclusion Criteria: Participants must be at least 18 years old, able to participate in informed consent, able to read, write, and speak English, gestation of at least 26 weeks at baseline (necessary because of short duration of study), and plan to give birth at XXX.

Exclusion Criteria: Participants will be excluded if they are actively psychotic or are currently incarcerated. Additionally, patients identified by medical staff as unable for medical reasons to currently participate in the study will not be approached for screening. Finally, only patients who indicate they are interested in participating in a study on doula support will be screened for the study.

Special Populations

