3.0 Study-Wide Number of Subjects

We plan to enroll 34 women in order to have a final number of 30 who complete the study.

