4.0 Study Timelines

4.1 Describe:

- *The duration of an individual subject's participation in the study.*
Between 4 weeks to 20 weeks, dependent upon fetal gestational age at baseline.
- *The duration anticipated to enroll all study subjects.*
12 months from the funding date
- *The estimated date for the investigators to complete this study (complete primary analyses)*
July 1, 2020

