5.0 Study Endpoints

Primary Outcomes

Relapse will be defined as percent drinking or drug use days postpartum and by drug screen at hospital admission results.

Postpartum PTSD severity – PTSD Checklist score

Postpartum depression severity – Edinburgh Postpartum Depression Scale Score

Breastfeeding Uptake

Neonatal Abstinence Syndrome

Length of NICU Stay

Secondary Outcomes

Social Support – NIH Toolbox

Labor and Delivery Autonomy

Participant Satisfaction

Doula Satisfaction

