a. Proposed sample size:

34

b. Proposed time period to be evaluated:

Initial prenatal visit to XXX Clinic for the current pregnancy through the postpartum visit.

c. How data will be analyzed and by whom:

Data will be analyzed by study staff, primarily the PI. The analyses to be conducted are the same as detailed in the analysis section of this protocol for the rest of the study above.

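### The fixed 365-day chart-review range in Section 20.0 is not reconciled with the per-participant chart period or the 12-month enrolment plan, so chart-based outcomes could be cut off

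*Combined protocol and SAP*

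**What the plan says.** Section 20.0 gives one calendar range: "Date range of the chart review 07/01/18 – 06/30/19". The Statistical Considerations that close the chart-review text (after 27.3) define the period differently in item b: "Initial prenatal visit to XXX Clinic for the current pregnancy through the postpartum visit". That item carries no calendar limit, and item a sets the sample at 34. This is the whole planned enrolment, since Section 3.0 states "We plan to enroll 34 women in order to have a final number of 30 who complete the study".

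Section 4.0 anticipates enrolment over "12 months from the funding date" and individual participation of "Between 4 weeks to 20 weeks, dependent upon fetal gestational age at baseline". It gives July 1, 2020 as the estimated date for completing the primary analyses. Section 14.0 says participants may ask for published results "following the end of the study period (after June 30, 2019"). The funding date appears nowhere, and no passage says which of these periods prevails.

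Section 6.0 makes the chart a source of both outcomes and covariates, and Section 12.0 (g) confirms that infant records will be used. Section 5.0 lists neonatal abstinence syndrome (NAS) and length of NICU stay as primary outcomes and defines relapse partly "by drug screen at hospital admission results". None of these three has an instrument in Table 1.

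**The concern.** A one-year range leaves no room for follow-up of women enrolled late in a one-year enrolment period. It also leaves no room for the prenatal records of women enrolled early. Whoever abstracts the charts has two instructions and no rule for choosing between them.

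If the calendar range is applied, the data at risk are those that evidently come only from the chart: NAS, NICU stay, the admission drug screen and prenatal covariates. This source is an inference, because no list of chart variables is given. The loss would fall on women at one or both ends of enrolment, in a study planning 15 completers per group whose purpose is to estimate effect sizes. Percent use days, PTSD, depression and breastfeeding are collected through Table 1 and are not affected.

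Section 27.3 has the link between identifiers and study IDs destroyed when the study closes. After that, a missed chart could not be matched to a participant.

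**Working it through.** The plan gives no total duration to reproduce. The spans below are derived from its dates.

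**1. Length of the range.** 07/01/18 to 06/30/19 inclusive is 365 days.

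**2. Span needed under Section 4.0, if enrolment uses the full 12 months.**
- Shortest: 365 + 4 × 7 = 393 days.
- Longest: 365 + 20 × 7 = 505 days.
- Excess over the range: 28 to 140 days.

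The 20 weeks is the protocol's own maximum. Section 2.0 requires "gestation of at least 26 weeks at baseline (necessary because of short duration of study"). A woman enrolled at 26 weeks who gives birth at 40 weeks reaches her 2-week visit after 14 + 2 = 16 weeks. On that basis the longest span is 365 + 112 = 477 days, still more than 365.

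**3. Reading A: the dates bound the records.** No 365-day range holds 393 days or more, so the conflict does not depend on the funding date. There is also a front-end problem. A woman at 26 weeks on 07/01/18 whose first visit was at 12 weeks (assumed) has records from 14 weeks earlier, 03/25/2018. With a first visit at 8 or 20 weeks (assumed), the dates are 02/25/2018 and 05/20/2018.

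**4. Reading B: the dates say when reviews are done.** Earlier prenatal records are then kept. To finish by 06/30/19, the last enrolment must be early enough:
- All women 4 weeks: 06/30/19 − 28 days = 06/02/2019, so 12-month enrolment must begin by 06/02/2018.
- 20 weeks: 06/30/19 − 140 days = 02/10/2019, so it must begin by 02/10/2018.

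If enrolment instead began on 07/01/18, the last woman would finish between 07/28/2019 and 11/17/2019.

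**5. Section 14.0.** It gives only an end date, so it conflicts with Section 4.0 only if funding fell after the start dates in step 4.

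**6. Illustrative loss of deliveries.** Assumptions: 34 women enrolled uniformly over 52 weeks from 07/01/18, birth at 40 weeks, and delivery D = participation − 2 weeks. The share delivering after 06/30/19 is E[D]/52. With this start date the figures apply on either reading.

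| Participation | Mean D (weeks) | Share after range | Of 34 |
|---|---|---|---|
| All 4 weeks | 2 | 2/52 = 0.038 | 1.3 |
| Uniform 4–16 weeks | 8 | 8/52 = 0.154 | 5.2 |
| All 16 weeks | 14 | 14/52 = 0.269 | 9.2 |

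**7. Sensitivity to the funding date (uniform 4–16 weeks).**
- Four weeks later: (8 + 4)/52 × 34 = 7.8 deliveries after the range.
- Eight weeks earlier, reading A: enrolment runs from week −8 to week 44. The share delivering before the range is E[(8 − D)⁺]/52 = 1.5/52, and the share after it is the same. That is 1.0 + 1.0 = 2.0 of 34.
- If every woman participates 12 weeks (D = 10) and funding is 10 weeks earlier, deliveries run from week 0 to week 52 and none is lost.
- On reading B, funding by 02/10/2018 gives no loss.

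**The case against.** The strongest reply is that the two chart-review entries answer different questions: Section 20.0 says when reviews are done, and the Statistical Considerations say which records are read. On that reading, funding by 02/10/2018 lets Sections 4.0, 14.0 and 20.0 and the per-participant period all hold. This stands as a possible reading. It leaves a gap, because no passage adopts it and none gives the funding date. If funding fell near 07/01/18, the charts of late enrolees are out of reach on either reading.

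Three stronger inferences are tempting and are not supported:
- **That the passages contradict one another on any reading.** They do so only if the Section 20.0 dates bound the records.
- **That some women must lose data whatever the funding date.** On reading A with uniform enrolment, at least 4/52 × 34 = 2.6 women have some time between baseline and follow-up outside the range, but the excluded part need not contain the delivery. On reading B the number can be zero.
- **That Section 14.0 flatly contradicts Section 4.0.** It gives an end date and no start. July 1, 2020 does not settle the matter, because analysis can properly follow the end of the study period.

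It is also fair to say that the 12 months is an anticipated duration, that faster enrolment would shorten the span, and that this pilot disclaims powered comparisons. These points limit the consequences but do not say which period the abstractor should use.

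**Conclusion.** The inconsistency is real and should be fixed. That the Section 20.0 range cannot contain 12 months of enrolment plus follow-up is certain if it bounds record dates. If it bounds review dates, the conflict depends on an unstated funding date, as does any conflict with Section 14.0.

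Confidence in actual data loss is only moderate. The estimate of about 5 of 34 deliveries (15%), with a range of about 1 to 9, rests on the Section 20.0 range being applied, uniform enrolment from 07/01/18, birth at 40 weeks and the assumed spread of participation. Later funding raises it, and earlier funding can bring it near zero. If the per-participant period is followed, no delivery is lost. The defect is therefore the missing rule, with possible loss of chart-based primary outcomes as its consequence.

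**What to change.** - In Section 20.0, replace the calendar range with the per-participant window already in the Statistical Considerations, for every enrolled woman. Extend it to infant discharge where NICU stay requires it.
- State the enrolment start date and reconcile Sections 4.0 and 14.0 with it.
- If an end date for the review is required, set it no earlier than 20 weeks after last enrolment. If enrolment ends 06/30/19, that is 06/30/19 + 140 days = 11/17/19, which leaves 227 days before July 1, 2020. Allow longer if an infant is still in hospital.
- Complete chart abstraction before the ID link is destroyed.

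The cost is a short IRB amendment and slightly later abstraction, with no new procedures. The sponsor should also check whether the consent form, which was not available for this review, states the same dates.
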